5.1.4. Discontinuation of Study Therapy

Subjects MUST be discontinued from study therapy AND withdrawn from the study for the following reasons:

- Withdrawal of informed consent (subject's decision to withdraw for any reason)
- Any clinical adverse event, laboratory abnormality or intercurrent illness which, in the opinion of the investigator, indicates that continued treatment with study therapy is not in the best interest of the subject
- Pregnancy
 - All WOCBP should be instructed to contact the investigator immediately if they suspect they might be pregnant (e.g., missed or late menstrual period) at any time during study participation. Institutional policy and local regulations should determine the frequency of on study pregnancy tests for WOCBP enrolled in the study.
 - The investigator must immediately notify the Sponsor in the event of a confirmed pregnancy in a patient participating in the study.
- Termination of the study by the Sponsor.
- Imprisonment or the compulsory detention for treatment of either a psychiatric or physical (e.g., infectious disease) illness.

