- The trial schema is represented in the following figure:

All individual patient registered into the trial should undergo the screening phase of the study. Patients consenting, registered and eligible will subsequently proceed through the treatment and follow up phases of the trial.

- **Screening Phase**

- It initiates after the written informed consent is obtained and the patients is registered. In this phase the assessment of the subject's eligibility to participate will be done, as determined by the inclusion/exclusion criteria.

- **Treatment Phase**

- Treatment will consist in the administration of ipilimumab and WBRT. The dose of ipilimumab will be 3 mg/kg, administered intravenously over a 90-minute period every 3 weeks, for a total of four doses. Standard WBRT should be initiated between the first and second dose of ipilimumab. The dose of radiation therapy will be 30 Gy over 10 fractions. Radiobiologically equivalent doses might be acceptable, but require discussion and approval of the Sponsor.
- Laboratory evaluations should be performed and the results examined before administration of each ipilimumab dose, with the exception of hormone results. For these latter parameters it is required that at least the results of the tests performed within the last 3 weeks are available and normal.
- As durable disease stabilization and/or objective tumor response can be seen after early progression before Week 12, it is recommended that, in the absence of dose-limiting toxicities

(eg, serious immune-mediated adverse reactions), all four doses of ipilimumab be administered over the initial 12 weeks even in the setting of apparent clinical progression, providing the subject's performance status remains stable.

- All subjects who enter the treatment period, including those who may have discontinued treatment for drug-related AEs and/or who have evidence of clinical progression during the induction period, should obtain a 12-week tumor assessment.
- Based on clinical experience in the ongoing and completed melanoma studies, the following recommendations apply for subject management in light of the Week 12 or later tumor assessments:

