 - The appearance of new lesions in subjects with other stable or shrinking baseline tumor burden may be experiencing clinical benefit and should continue in follow-up and/or maintenance therapy before alternative anti-cancer agents are considered. These subjects can be seen to have continued tumor shrinkage in follow-up scans.
 - As long as overall tumor burden is stable or decreasing, subjects should remain in follow-up, even in the presence of new lesions.
 - Clinical progression warranting alternative anti-cancer treatment should be considered only in subjects whose overall tumor burden appears to be substantially increased and/or in subjects whose performance status is decreased.
- **Follow-up** (duration of study).
 - Subjects who are no longer receiving ipilimumab because of unacceptable toxicity (refractory Grade > 3 immune-mediated adverse reactions) or due to investigator judgment are managed in follow-up. Efficacy assessments for these subjects during follow-up are as per the standard of care. Date of death is recorded.
 - Subjects who discontinue ipilimumab treatments should be followed until death or the closure of the study (whichever is first).
 - Subjects who are no longer receiving ipilimumab because of clinical progression and who have switched to alternative treatment are not followed formally except to record the date of death.

Study duration:

- For each individual patient, the maximal duration of the treatment period is 4 cycles of ipilimumab. Patients will be followed up until death or trial termination (whatever comes first), for a maximum of 36 months. The study will be terminated 18 months after the last patient received the first dose of ipilimumab.

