5.1.5. Permanent Discontinuation of Ipilimumab

5.1.5.a Permanent Discontinuation for Related Adverse Events

Permanently discontinue ipilimumab for any of the following:

- Persistent moderate adverse reactions or inability to reduce corticosteroid dose to 7.5 mg prednisone or equivalent per day (due to an AE).
- Failure to complete full treatment course within 18 weeks from administration of first dose.
- Severe or life-threatening adverse reactions, including any of the following:
 - Colitis with abdominal pain, fever, ileus, or peritoneal signs; increase in stool frequency (7 or more over baseline), stool incontinence, need for intravenous hydration for more than 24 hours, gastrointestinal hemorrhage, and gastrointestinal perforation
 - Aspartate aminotransferase (AST) or alanine aminotransferase (ALT) >5 times the upper limit of normal or total bilirubin >3 times the upper limit of normal
 - Stevens-Johnson syndrome, toxic epidermal necrolysis, or rash complicated by full thickness dermal ulceration, or necrotic, bullous, or hemorrhagic manifestations
 - Severe motor or sensory neuropathy, Guillain-Barré syndrome, or myasthenia gravis
 - Severe immune-mediated reactions involving any organ system (eg, nephritis, pneumonitis, pancreatitis, non-infectious myocarditis)
 - Immune-mediated ocular disease that is unresponsive to topical immunosuppressive therapy

- Any adverse event, laboratory abnormality or intercurrent illness which, in the judgment of the investigator, presents a substantial clinical risk to the patient with continued dosing.
- The development of progression (irPD) in the global tumor burden confirmed by serial imaging 4-6 weeks later and/or clinical deterioration of subject's condition such that further benefit from ipilimumab dosing is unlikely or requires a change of therapy.

Please refer to the IB for specific treatment algorithms.

The following neurological adverse event requires permanent discontinuation of ipilimumab and defines unacceptable neurotoxicity:

- Any motor neurologic toxicity \geq Grade 3 regardless of causality
- Any \geq Grade 3 treatment related sensory neurologic toxicity

Please refer to the IB for specific treatment algorithms.

5.1.5.b Exceptions to Permanent Discontinuation

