End of treatment visit (EOT) will take place 30 + 2 days after the last dose of ipilimumab. This visit will require a complete evaluation of patient's symptoms, Karnofsky/Barthel scores, physical exam (including weight, vital constants and neurological exam), lab tests, collection of AEs and of concomitant medication. If the disease was not evaluated before, EOT visit should include a body and cranial CTscan/MRI.

6.2.1.e Follow-up visits.

Per protocol, the disease should be evaluated until death or confirmed progression (mWHO/immune response criteria). Tumor assessment will be performed with CT/MRI of brain, chest, abdomen and pelvis at baseline, at weeks 12 and 17 \pm 1 and then, every 9 \pm 1 weeks. The same method of assessment (CT or MRI) should be used throughout the patient's time on study for consistent evaluation of response.

After EOT visit, the occurrence of new SAEs and irAEs will be reported up to 90 days after last ipilimumab administration. Ongoing SAEs/irAEs will be followed up until recovery.

Survival status will be checked at week 12, 16-18 and then, every 8-10 weeks.

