6.2.2. Study Completion or Early Discontinuation Visit

At the time of study early withdrawal, the reason for early withdrawal and any new or continuing adverse events should be documented.

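### Section 5.1.4 withdraws adverse-event stops from the study while Section 3 keeps overlapping patients in survival follow-up, so 1-year vital status could be lost for some evaluable patients

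*Protocol*

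**What the plan says.** Protocol 5.1.4 opens its list with "Subjects MUST be discontinued from study therapy AND withdrawn from the study for the following reasons". The list contains consent withdrawal, pregnancy, termination by the sponsor and detention. It also contains the item beginning "Any clinical adverse event, laboratory abnormality or intercurrent illness which, in the opinion of the investigator", which applies when the investigator considers continued study therapy not to be in the patient's interest.

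Protocol Section 3 (Study Design) treats overlapping patients differently:

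- Under Follow-up, patients off ipilimumab for unacceptable toxicity or investigator judgment are managed in follow-up and their date of death is recorded. It adds: "Subjects who discontinue ipilimumab treatments should be followed until death or the closure of the study (whichever is first".
- Under Study duration: "Patients will be followed up until death or trial termination (whatever comes first), for a maximum of 36 months".
- Under Treatment Phase, the week-12 tumour assessment is asked of "All subjects who enter the treatment period, including those who may have discontinued treatment for drug-related AEs", among others.

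Two further places bear on the question. Section 5.1.5.a lists, as a ground for permanently stopping ipilimumab, "Any adverse event, laboratory abnormality or intercurrent illness which, in the judgment of the investigator, presents a substantial clinical risk"; it does not mention study status. Section 8.3.4 requires the protocol's discontinuation and follow-up procedures to be carried out in a patient who becomes pregnant, unless pregnancy contraindicates them. Pregnancy is itself a 5.1.4 withdrawal reason.

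Survival contacts are already planned. Section 6.2.1.e says "Survival status will be checked at week 12, 16-18 and then, every 8-10 weeks", and Section 9.3.1 sets a minimum of every 12 weeks from the first dose.

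**The concern.** The primary endpoint is the actual proportion of patients alive 1 year after the first ipilimumab dose (Section 9.4.2.1). It is judged by whether at least 17 of 56 evaluable patients survive that long (Section 9.1). A patient is evaluable after at least one ipilimumab dose and full whole-brain radiotherapy (Section 9.2), so stopping later for toxicity does not remove anyone from the denominator.

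If a site reads 5.1.4 as written, a patient stopped for an adverse event leaves the study and may have no further survival contact. The patient still counts in the 56, but nobody may know whether he or she was alive at 1 year. The design has little slack: its exact power is only just above the stated 80%, so even one such patient matters. Status missed during the trial may be hard to recover afterwards.

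**Working it through.** **1. The rules side by side, for a patient stopped on the investigator's judgment of an adverse event**

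| Place | Study therapy | Study participation |
|---|---|---|
| 5.1.4 | stop | withdrawn, mandatory |
| Section 3, Follow-up | already stopped | followed to death or closure; date of death recorded |
| Section 3, Treatment Phase | already stopped (drug-related events) | week-12 assessment still expected |
| 5.1.5.a | stop ipilimumab | silent |
| 8.3.4 (pregnancy only) | stop | follow-up procedures continue |

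The first row conflicts with the second and third. The fourth does not contradict 5.1.4. However, its similar trigger means that one event can fall under either section, and nothing says which governs. The fifth suggests that withdrawal was not meant to end follow-up, but it covers pregnancy only.

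**2. Who can affect the endpoint**

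Only evaluable patients can. Radiotherapy starts no later than the day of the second dose and is planned as 10 daily fractions, so a patient stopped around dose 3 or 4 would normally have completed it and be evaluable. A patient withdrawn before completing radiotherapy is not evaluable and cannot affect 17 of 56.

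**3. Reproducing the design**

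Inputs from Section 9.1: null rate 0.20, alternative 0.35, n = 56, success at 17 or more. With X binomial:

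- False-positive rate: P(X ≥ 17 | 56, 0.20) = 0.0432.
- Power: P(X ≥ 17 | 56, 0.35) = 0.8064.

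The smallest n with exact one-sided error at most 0.05 and power at least 0.80 is 56, with cut-off 17. The plan's figures reproduce.

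**4. Illustration of lost status**

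The number lost, k, is an assumption. Assume also that unknown status is not counted among the 17 and that loss is unrelated to outcome. Then 17 survivors must be found among the 56 − k patients with known status:

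probability of success = P(X ≥ 17 | 56 − k, p)

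| k unknown | known n | power (p = 0.35) | false-positive rate (p = 0.20) |
|---|---|---|---|
| 0 | 56 | 80.6% | 4.3% |
| 1 | 55 | 78.0% | 3.7% |
| 2 | 54 | 75.1% | 3.1% |
| 3 | 53 | 71.9% | 2.6% |

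The ceiling of 4.3% does not depend on why patients are lost. If unknowns are not counted as alive, the counted survivors cannot exceed the true survivors, so the count cannot reach 17 unless the truth does.

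**The case against.** The strongest reply is that the protocol, taken as a whole, leans towards continued follow-up. Section 3 addresses these patients directly and in several sentences. Even patients who switch to another treatment have their date of death recorded. Section 8.3.4 continues follow-up for another 5.1.4 reason. Against this stands one header sentence over a mixed list, with withdrawal from the study left undefined. A site would have to set aside several explicit instructions to lose vital status. This stands as a reason to call the loss possible rather than expected. It does not remove the conflict: the 5.1.4 wording is mandatory, the adverse-event reason shares its list with reasons that plausibly do end participation, and no text says that survival contact continues after an adverse-event withdrawal.

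A reader might infer four stronger things that the documents do not support.

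- **That 5.1.5.a contradicts 5.1.4.** It is silent on study status. It also sits under a heading about related events and concerns ipilimumab, whereas 5.1.4 covers any cause and study therapy generally.
- **That Section 6.2.2 is deficient because it asks only for "the reason for early withdrawal and any new or continuing adverse events should be documented".** A patient seen at that visit is alive that day, the case report form is not among the documents, and an entry made at withdrawal would not secure status at 1 year.
- **That the trial could wrongly claim efficacy through this route.** On the plain reading of Sections 9.1 and 9.4.2.1, a patient not known to be alive is not one of the 17, so the error rate can only fall.
- **That the several 1-year rates in SAP Tables 18 and 19 are part of this defect.** Which of them is compared with 17 of 56 concerns unknown status from any cause and is a separate point. The protocol already names the actual proportion.

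**Conclusion.** The point holds as an internal inconsistency. Confidence is high that 5.1.4 and Section 3 give incompatible instructions for overlapping patients, and lower that this would affect the primary endpoint. Sites that follow Section 3 lose nothing, and nothing is lost where a death within the year becomes known anyway.

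If status is lost, the cost is power. With one unknown patient, power is 78.0%, already below the planned 80%; with three it is 71.9%. These figures rest on assumed counts, on loss unrelated to outcome, and on unknown status not counting as alive. The fall would be larger if those lost were more likely than average to be survivors, and smaller if less likely. It would be wrong to conclude that all adverse-event stops will be lost, or that the design as stated is underpowered.

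**What to change.** Reconcile Section 5.1.4 with Section 3 and Section 8.3.4:

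1. In 5.1.4, separate discontinuing study therapy, with the existing reasons unchanged, from withdrawing from the study.
2. State that patients who stop therapy for an adverse event, laboratory abnormality or intercurrent illness remain in the survival follow-up already scheduled in Sections 6.2.1.e and 9.3.1.

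No change to when or why treatment stops is proposed. The cost is a few sentences in a protocol amendment and a note to sites; no new visits or contacts are needed.

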5.1.5. Permanent Discontinuation of Ipilimumab

5.1.5.a Permanent Discontinuation for Related Adverse Events

Permanently discontinue ipilimumab for any of the following:

- Persistent moderate adverse reactions or inability to reduce corticosteroid dose to 7.5 mg prednisone or equivalent per day (due to an AE).
- Failure to complete full treatment course within 18 weeks from administration of first dose.
- Severe or life-threatening adverse reactions, including any of the following:
 - Colitis with abdominal pain, fever, ileus, or peritoneal signs; increase in stool frequency (7 or more over baseline), stool incontinence, need for intravenous hydration for more than 24 hours, gastrointestinal hemorrhage, and gastrointestinal perforation
 - Aspartate aminotransferase (AST) or alanine aminotransferase (ALT) >5 times the upper limit of normal or total bilirubin >3 times the upper limit of normal
 - Stevens-Johnson syndrome, toxic epidermal necrolysis, or rash complicated by full thickness dermal ulceration, or necrotic, bullous, or hemorrhagic manifestations
 - Severe motor or sensory neuropathy, Guillain-Barré syndrome, or myasthenia gravis
 - Severe immune-mediated reactions involving any organ system (eg, nephritis, pneumonitis, pancreatitis, non-infectious myocarditis)
 - Immune-mediated ocular disease that is unresponsive to topical immunosuppressive therapy

- Any adverse event, laboratory abnormality or intercurrent illness which, in the judgment of the investigator, presents a substantial clinical risk to the patient with continued dosing.
- The development of progression (irPD) in the global tumor burden confirmed by serial imaging 4-6 weeks later and/or clinical deterioration of subject's condition such that further benefit from ipilimumab dosing is unlikely or requires a change of therapy.

Please refer to the IB for specific treatment algorithms.

The following neurological adverse event requires permanent discontinuation of ipilimumab and defines unacceptable neurotoxicity:

- Any motor neurologic toxicity \geq Grade 3 regardless of causality
- Any \geq Grade 3 treatment related sensory neurologic toxicity

Please refer to the IB for specific treatment algorithms.

5.1.5.b Exceptions to Permanent Discontinuation

- Potentially reversible inflammation ($<$ Grade 4), attributable to a local anti-tumor reaction and a potential therapeutic response. This includes inflammatory reactions at sites of tumor resections or in draining lymph nodes, or at sites suspicious for, but not diagnostic of metastasis.
- Hospitalization for \leq Grade 2 adverse events where the primary reason for hospitalization is to expedite the clinical work-up.
- Patients with the following conditions where in the investigator's opinion continuing study drug administration is justified:
 - Ocular toxicity that has responded to topical therapy.
 - Endocrinopathies where clinical symptoms are controlled with appropriate hormone replacement therapy. **Note:** Ipilimumab may not be restarted while the patient is being treated for this toxicity with systemic corticosteroids, except for patients on stable doses of hormone replacement therapy such as hydrocortisone.

5.1.6. Immune-Related Adverse Events (irAEs) Reactions and Immune-mediated Adverse Reactions: Definition, Monitoring, and Treatment

Blocking CTLA-4 function may permit the emergence of auto-reactive T cells and resultant clinical autoimmunity. Rash/vitiligo, diarrhea/colitis, uveitis/episcleritis, hepatitis, and hypopituitarism were drug-related, presumptive autoimmune events, now termed immune-mediated adverse reactions, noted in previous ipilimumab studies.

For the purposes of this study, an immune-related adverse reaction is defined as an adverse reaction of unknown etiology associated with drug exposure and consistent with an immune phenomenon. Efforts should be made to rule out neoplastic, infectious, metabolic, toxin or other etiologic causes prior to labeling an event an immune-related adverse reactions. Serologic, immunologic, and histologic (biopsy) data should be used to support the diagnosis of an immune-related toxicity. Suspected immune-related adverse reactions must be documented on an AE or SAE form. Another term for an irAE is an

immune-mediate adverse reaction, as it is termed in both FDA and EMA approved Prescribing Information. Both terms may be used in this protocol document.

Patients should be informed of and carefully monitored for evidence of clinically significant systemic immune-mediated adverse reactions (e.g., systemic lupus erythematosus-like diseases) or organ-specific immune-mediated adverse reaction (e.g., rash, colitis, uveitis, hepatitis or thyroid disease). If an immune-mediated adverse reaction is noted, appropriate work-up (including biopsy if possible) should be performed, and steroid therapy may be considered if clinically necessary.

It is unknown if systemic corticosteroid therapy has an attenuating effect on ipilimumab activity. However, clinical anti-tumor responses have been maintained in patients treated with corticosteroids and discontinued from ipilimumab. If utilized, corticosteroid therapy should be individualized for each patient. Prior experience suggests that colitis manifested as \geq Grade 3 diarrhea requires corticosteroid treatment.

Specific treatment algorithms for immune-mediated adverse reactions adverse events are included as appendices in the IB.

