5.1.7. Other Guidance

In patients experiencing neurological deterioration due to an increase of either the tumor mass or the peritumoral edema, the decision to maintain or not ipilimumab will be done case by case on the basis of clinical judgement and discussion with the Sponsor.

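### A grade 3 or higher motor event caused by tumour growth or oedema falls under a mandatory stop in protocol 5.1.5.a and a case-by-case decision in 5.1.7

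*Protocol*

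**What the plan says.** Protocol 5.1.5.a carries the heading "Permanent Discontinuation for Related Adverse Events". Near its end it sets a separate neurological rule: "The following neurological adverse event requires permanent discontinuation of ipilimumab and defines unacceptable neurotoxicity". Two items follow.

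- The motor item applies to any motor neurologic toxicity at or above "Grade 3 regardless of causality".
- The sensory item has the same grade threshold but is confined to "treatment related sensory neurologic toxicity".

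Section 5.1.5.b lists the exceptions to permanent discontinuation. The nearest to this topic is potentially reversible inflammation below grade 4 that is put down to a local anti-tumour reaction. Growth of the brain lesions is not listed, and there is no pointer to 5.1.7.

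Section 5.1.7 opens "In patients experiencing neurological deterioration due to an increase of either the tumor mass or the peritumoral edema" and continues "the decision to maintain or not ipilimumab will be done case by case on the basis of clinical judgement and discussion with the Sponsor". It sets no grade limit, does not set motor events aside, and does not refer back to 5.1.5.

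**The concern.** Every patient in this trial has brain metastases, and protocol section 1.2.1 names focal neurologic deficits among the typical presentations. A motor deficit from a growing lesion or its oedema is therefore a foreseeable event. For that event one section removes discretion and another grants it.

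Three things are at stake. The first is the management of the individual patient, because following one section can mean departing from the other. The second is treatment exposure, a secondary feasibility objective in section 2.2, which SAP section 1.3 summarises by number of ipilimumab cycles, omissions, reductions and delays. The third is the by-subject listing of adverse events leading to discontinuation in protocol 9.4.3. The second and third could vary with the section that a site happened to apply.

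There is also a labelling question. As worded, 5.1.5.a gives a disease-caused motor event the name of unacceptable neurotoxicity, under a heading restricted to related events.

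**Working it through.** No calculation applies: the point concerns two text rules, and the plan states no figure for it. The check is whether one event can satisfy both rules, and whether anything in the documents ranks one above the other.

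**Step 1: does the motor item reach disease-caused events?** The word toxicity might suggest drug causation. Three things point the other way. The item sets causality aside expressly. The sensory item beside it is limited to treatment-related events, so the difference is explicit. The rule calls its subject an adverse event, and section 8.1 defines an adverse event without requiring any relationship to the product. The item therefore reaches disease-caused events, against the section's own heading.

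**Step 2: does 5.1.7 reach grade 3 or higher motor events?** It is defined by cause (tumour mass or oedema), with no limit by grade or by type of deficit. It does.

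**Step 3: does the exceptions list resolve the overlap?** The cases line up as follows.

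| Neurological event and attributed cause | 5.1.5.a neurological items | 5.1.5.b exception | 5.1.7 | Result |
|---|---|---|---|---|
| Motor, grade 3 or 4, tumour growth | Stop | None listed | Case by case | Conflict |
| Motor, grade 4, oedema | Stop | Not available (below grade 4 only) | Case by case | Conflict |
| Motor, grade 3, oedema not judged an anti-tumour reaction | Stop | None listed | Case by case | Conflict |
| Motor, grade 3, oedema judged a reversible anti-tumour reaction | Stop | May apply | Case by case | Possibly resolved |
| Sensory, grade 3 or higher, tumour or oedema, not treatment related | Not triggered | Not needed | Case by case | No conflict from these items |
| Motor, below grade 3, tumour or oedema | Not triggered | Not needed | Case by case | No conflict from these items |

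**Step 4: does either section take precedence?** Neither cites the other and no order is stated.

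**Step 5: what does it touch downstream?** Section 9.2 makes a patient evaluable after at least one ipilimumab dose and the full WBRT course. Stopping later ipilimumab doses therefore does not change who is counted, and the threshold of 17 one-year survivors among 56 evaluable patients stays as it is. The exposure summary and the discontinuation listing can change. If 56 patients are treated, each patient handled differently moves an exposure percentage by 1/56 = 1.8 percentage points.

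**The case against.** The best counter-reading is that 5.1.7 is the specific provision for tumour- or oedema-caused worsening and so overrides the general rule. That may be the intention. The text does not say so, and 5.1.5.b, where an override would be expected, does not list it.

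Sponsor contact is a real safeguard. Section 5.1.7 requires discussion with the sponsor, and section 5.1.3 asks investigators to contact the sponsor about any adverse event prompting a skipped dose or discontinuation. This makes divergence between sites less likely, so the fair statement is that sites could differ, not that they would. It still leaves the sponsor without one written rule to apply.

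Disregarding causality may be a deliberate conservative choice, since 5.1.3 does the same for grade 3 or higher skin events. That choice is not criticised here; only its collision with 5.1.7 is. For some patients both routes also end the same way, because the case-by-case decision is to stop or because the separate clinical-deterioration item in 5.1.5.a applies.

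A reader might infer more than the documents support, in three ways.

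- **That section 3 is a third conflicting rule.** It recommends that "all four doses of ipilimumab be administered over the initial 12 weeks even in the setting of apparent clinical progression", but only in the absence of dose-limiting toxicity and with stable performance status. A conditional recommendation does not contradict a mandatory stop, and a grade 3 motor deficit may well fail those conditions.
- **That the trial cannot tell whether the combination is neurotoxic.** Section 8.2 requires a related or not-related call for adverse events. Section 9.4.3 tabulates all and drug-related events separately and adjudicates immune-mediated reactions by ruling out causes such as tumour progression. SAP sections 1.6 and 1.7 keep treatment-related toxicities apart from all adverse events. A motor event judged unrelated would appear among all events, not among toxicities, whichever stopping rule was used.
- **That the number of affected patients can be estimated.** An assumed rate of 5 to 15% would give 0.05 × 56 = 2.8 to 0.15 × 56 = 8.4 patients, but nothing in the documents anchors that range. The figure of up to 95% in section 1.2.1 concerns brain lesions contributing to death, not motor deficits during dosing.

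**Conclusion.** The contradiction is real and confined to sections 5.1.5.a, 5.1.5.b and 5.1.7. A grade 3 or higher motor event attributed to tumour growth, or to oedema outside the 5.1.5.b exception, falls under both a mandatory stop and a discretionary decision. The documents do not say which governs.

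Its size cannot be stated, because they give no rate for such events. The consequences are possible inconsistency in patient management, in treatment exposure and in the discontinuation listing, together with an unclear label for disease-caused events. The primary decision rule is not affected.

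The conclusion rests on reading the causality wording as it stands and on the absence of any cross-reference or stated order between the sections. It takes no view on which rule is clinically right. It is a correction that should be made, not one on which the primary analysis depends.

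**What to change.** Amend 5.1.5.a, 5.1.5.b and 5.1.7 together so that a single rule, chosen by the sponsor, governs grade 3 or higher motor events attributed to tumour growth or peritumoral oedema. Add a cross-reference between the sections. Bring the heading of 5.1.5.a into line with its content, since it is now limited to related events while the motor item is not. State whether disease-caused motor events count as unacceptable neurotoxicity. Section 3 needs no change for this point.

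Optionally, record the attributed cause (tumour or oedema, WBRT, ipilimumab, other) of each grade 3 or higher neurological event. Section 8.2 asks only whether an event is related to the investigational product, so this would add detail, but the related/all split in the tables does not depend on it.

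The cost is a wording amendment to three short sections and, if the option is taken, one field on the adverse event page. Sample size and primary analysis stay as they are.
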